11.	ADMINISTRATIVE ASPECTS, MONITORING AND PUBLICATION	30
11.1	Handling and storage of data and documents.....	30
11.2	Monitoring and Quality Assurance	30
11.3	Amendments	30
11.4	Annual progress report.....	30
11.5	Temporary halt and (prematurely) end of study report	31
11.6	Public disclosure and publication policy	31
12.	STRUCTURED RISK ANALYSIS	32
12.1	Potential issues of concern.....	32
12.2	Synthesis.....	32
13.	REFERENCES	33
14.	Appendix A: Instruction saliva collection.....	36
14.1	Speeksel-wat: voor kinderen die nog niet zelf in een buisje kunnen spugen.	36
14.2	Speeksel-spuug setje: voor grotere kinderen die zelf in een buisje kunnen spugen	37

LIST OF ABBREVIATIONS AND RELEVANT DEFINITIONS

ABR	General Assessment and Registration form (ABR form), the application form that is required for submission to the accredited Ethics Committee; in Dutch: Algemeen Beoordelings- en Registratieformulier (ABR-formulier)
AE	Adverse Event
API	Application Programming Interface
CA	Competent Authority
CCMO	Central Committee on Research Involving Human Subjects; in Dutch: Centrale Commissie Mensgebonden Onderzoek
CADD	Combined Annotation Dependent Depletion
COPP	'Clinical features of COVID-19 in Pediatric Patients' study
COPP2	'Clinical features of COVID-19 in Pediatric Patients, long term effects' study
COPP-IMM	'COVID-19 in Pediatric Patients: clinical and immunological features' study
COVID-19	COronaVirus Disease 2019
CRF	Case Record Form
CV	Curriculum Vitae
DNA	DeoxyriboNucleic Acid
DSMB	Data Safety Monitoring Board
EU	European Union
EudraCT	European drug regulatory affairs Clinical Trials
FDR	False Discovery Rate
Gb	Gigabyte
GCP	Good Clinical Practice
GDPR	General Data Protection Regulation; in Dutch: Algemene Verordening Gegevensbescherming (AVG)
gnomAD	Genome Aggregation Database
GoNL	Genome Of the Netherlands
IB	Investigator's Brochure
IC	Informed Consent
IEI	Inborn Error of Immunity
IUIS	International Union of Immunological Societies
MAF	Minor Allele Frequency
METC	Medical research ethics committee (MREC); in Dutch: medisch-ethische toetsingscommissie (METC)
MIS-C	Multi-system Inflammatory Syndrome in Children
NGS	Next Generation Sequencing
PICU	Pediatric Intensive Care Unit
PROMs	Patient Reported Outcome Measures
QC	Quality Control
QV	Qualifying Variants
RNA	RiboNucleic Acid
RT-PCR	Reverse Transcriptase Polymerase Chain Reaction

(S)AE	(Serious) Adverse Event
SARS-CoV-2	Severe Acute Respiratory Syndrome CoronaVirus 2
Sponsor	The sponsor is the party that commissions the organisation or performance of the research, for example a pharmaceutical company, academic hospital, scientific organisation or investigator. A party that provides funding for a study but does not commission it is not regarded as the sponsor, but referred to as a subsidising party.
SUSAR	Suspected Unexpected Serious Adverse Reaction
UAVG	Dutch Act on Implementation of the General Data Protection Regulation; in Dutch: Uitvoeringswet AVG
WES	Whole Exome Sequencing
WHO	World Health Organisation
WMO	Medical Research Involving Human Subjects Act; in Dutch: Wet Medisch-wetenschappelijk Onderzoek met Mensen

SUMMARY

Rationale:

Following infection with SARS-CoV-2, some children develop the potentially life-threatening disease Multi-System Inflammatory Syndrome in Children (MIS-C) and some children develop post-COVID condition (formerly 'long COVID'). It is unknown why some children develop severe or prolonged symptoms after SARS-CoV-2 infection, while most children have asymptomatic or mild disease. We hypothesize that rare variants in genes associated with the immune system predispose children to develop MIS-C or post-COVID condition after infection with SARS-CoV-2.

Objective:

Primary objective: To identify rare, high impact genetic variants in immunological genes and pathways in children with a history of MIS-C or pediatric post-COVID condition.

Secondary objectives: To analyze the clinical characteristics and long-term effects of pediatric COVID-19 and MIS-C. To characterize the functional and clinical impact of genetic variants in MIS-C and post-COVID condition and identify targets for therapy.

Study design:

We will do an observational study. We will perform Whole Exome Sequencing (WES) using Next Generation Sequencing (NGS) on DNA from blood or saliva. We will include: (1) MIS-C cases: Children with a history of MIS-C; (2) post-COVID condition cases: Children with post-COVID condition; and (3) Controls: SARS-CoV-2 exposed age-matched control group: children who were infected with SARS-CoV-2 but did not develop moderate to severe COVID-19, MIS-C or post-COVID condition. We will do immunological analyses to validate the results of the genetic study. We will evaluate if certain genetic risk factors aggregate in specific subgroups of patients.

Study population:

Children 0-19 years old with a history of MIS-C (n=100), post-COVID condition (n=100), or uncomplicated SARS-CoV-2 infection (n=200).

Main study parameters/endpoints:

- Individual analysis of immunological genes in cases only: We will restrict our analysis to pathogenic (class 5) or likely pathogenic (class 4) variants in genes known to be associated with monogenic inborn errors of immunity to diagnose previously unsuspected inborn errors of immunity (IEI) in MIS-C or post-COVID condition cases.
- Case-control study: We will evaluate if a larger proportion of cases with MIS-C or post-COVID condition have rare and presumably deleterious variants in immunological genes than children with an asymptomatic or mild infection.

Nature and extent of the burden and risks associated with participation, benefit and group relatedness:

Results of this study are related to the target group (i.e. children with SARS-CoV-2 infection). Children with MIS-C or post-COVID condition participating in this study may benefit directly, if an immunological condition is identified that warrants treatment or follow-up. Controls will not directly benefit from this study, since genetic data from the controls is analyzed at 'group level' in the case-control study. To minimize burden we will send participants a saliva DNA home collection kit. These can be returned by regular mail. Samples for the immunological studies have already been collected and stored.

1. INTRODUCTION AND RATIONALE

Most children infected with SARS-CoV-2 have little or no symptoms, but some children develop life-threatening or long-term post-infectious complications. Among these post-infectious sequelae are multi-system inflammatory syndrome in children (MIS-C) and post-COVID condition (formerly also known as 'long COVID'). MIS-C is a potentially life-threatening hyperinflammatory post-infectious disease that occurs in 1:2000 to 1:5000 children three to six weeks after infection with SARS-CoV-2 (1, 2). MIS-C is predominantly a childhood disease, but occasionally, (young) adults develop multi-system inflammatory syndrome (MIS-A) (3). Patients with MIS-C present with a high fever, frequent cardiac and gastrointestinal involvement, neurological symptoms and show high C-reactive protein levels (4, 5). About fifty percent of children with MIS-C are admitted to pediatric intensive care units (PICUs) because of cardiogenic or distributive shock (6). Most children respond well to anti-inflammatory treatment, but 1-2% of children with MIS-C die (7, 8). Children with MIS-C have profound immune dysregulation, with lymphopenia, T-cell receptor skewing, increased plasmablasts, a broad range of auto-antibodies, very high cytokine levels and activated monocytes (9-14). A subset of children with MIS-C demonstrate polyclonal expansion of TRBV11-2 skewing, suggesting superantigenic stimulation (15-17). Although the immunological profile of MIS-C is being uncovered, it is still not understood why some children develop MIS-C after SARS-CoV-2 infection while most children don't.

In addition to the life-threatening post-infectious complication MIS-C, children can develop post-COVID condition following infection with SARS-CoV-2 (18-22). Symptoms include fatigue, headache, cough, dyspnea or 'brain fog' and may last for months following the initial infection. The etiology of post-COVID condition is unknown, but similar to MIS-C, it may be a result of immunological dysregulation following infection with SARS-CoV-2 (23, 24).

Many children have been infected with SARS-CoV-2 since the beginning of the pandemic, but both MIS-C and pediatric post-COVID condition are relatively rare diseases. **Our hypothesis is, that rare variants in genes associated with the immune system predispose children to develop MIS-C or post-COVID condition after infection with SARS-CoV-2** (25). Identifying rare inborn errors of immunity in these children will guide proper treatment and counsel the patients and their families. In addition, by comparing the prevalence of genetic immunological variants in children with a complicated vs. uncomplicated course of SARS-CoV-2 infection, we will gain insight into the pathogenesis of these diseases.

Our hypothesis is supported by several lines of evidence. Kawasaki Disease, a disease with resemblances to MIS-C, is more prevalent in Asian populations and is associated with variants in *FCGR2A* and *ITPKC* (26-28). Variants in immunological genes have been reported in 3/18 MIS-C patients (in *XIAP*, *CYBB* and *SOCS1*) (29, 30). Mutations in these genes cause different severe immunodeficiencies, suggesting that MIS-C may be the first sign of an inborn error of immunity in a significant proportion of children. Similarly, in a subset of adults with life-threatening COVID-19, inborn errors of type I interferon immunity have been found (31, 32). Although MIS-C and severe acute COVID-19 are different entities, both are characterized by a dysfunctional, massive hyperinflammatory response and both are apparently associated with previously unsuspected inborn errors of immunity.

1.1 OBJECTIVES

1.1.1 Primary objective:

To identify rare, high impact genetic variants in immunological genes and pathways in children with a history of MIS-C or pediatric post-COVID condition

1.1.2 Secondary objectives:

To analyze the clinical characteristics and long-term effects of pediatric COVID-19 and MIS-C

[figure not shown]
To characterize the functional and clinical impact of genetic variants in MIS-C and post-COVID condition and identify targets for therapy

2. STUDY DESIGN

To identify rare, high impact genetic variants in immunological genes in MIS-C and pediatric post-COVID condition we will do a single center **observational study**. Cases and controls will be recruited by the principal investigators of other studies on pediatric COVID and MIS-C. We will perform Whole Exome Sequencing (WES) using Next Generation Sequencing (NGS) on DNA from blood or saliva in:

- (1) **MIS-C cases:** Children with a history of MIS-C (n=100);
- (2) **post-COVID condition cases:** Children with post-COVID condition (n=100); and
- (3) **controls:** SARS-CoV-2 exposed age-matched control group (n=200): children who were infected with SARS-CoV-2 but did not develop moderate to severe COVID-19, MIS-C or post-COVID condition

[figure not shown]
Since all patients and controls have already been included in other studies, we expect to be able to include all participants before January 2024.

3. STUDY POPULATION

3.1 Population (base)

In this study we will include children until 19 years of age.

1. Children in group (1): MIS-C, will be recruited from the ongoing COPP, COPP-IMM, WKZ and Kawasaki studies.
2. Children in group (2): post-COVID condition, will be recruited from the COPP follow-up study 'COPP2', the PoCoCoChi study (Post Corona Complaints in Children), the VINCERO/VINCERE study (vaccination study in 'long COVID') and the POCOS (Post COVID) clinical observational study.
3. Children in group (3): 'Exposed' control group, will be recruited from the COPP-study, the CoKIDS study, PoCoCoChi study, de CORONATHuisstudie and the SARSLIVA study.

We will recruit subjects from the respective studies based on prior consent to be approached for additional studies.

3.2 Inclusion criteria

In order to be eligible to participate in this study, a subject must meet all of the following criteria, depending on group:

1. Children (<19 years) with a history of MIS-C: as defined according to WHO criteria [36]
2. Children (<19 years) with post-COVID condition: as defined according to the WHO case definition [37].
This includes a history of probable or confirmed prior SARS-CoV-2 infection, with signs and symptoms (including fatigue, shortness of breath, cognitive dysfunction) that are present after 12 weeks, last at least 2 months, have an impact on daily functioning and are not explained by an alternative diagnosis.
3. 'Exposed' control group: children (<19 years of age): a history of proven SARS-CoV-2 infection (RT-PCR, antigen test or serology positive)

3.3 Exclusion criteria

A potential subject who meets any of the following criteria will be excluded from participation in this study:

1. Group 1 (MIS-C): no specific exclusion criteria

2. Group 2 (post-COVID condition): other plausible cause of symptoms AND/OR a history compatible with chronic fatigue syndrome prior to infection with SARS-CoV-2. Children with a history of MIS-C who suffer prolonged signs and symptoms will be included in the MIS-C group.
3. Group 3 ('exposed' control group): MIS-C or post-COVID condition; AND/OR Moderate or severe course of COVID-19, as defined in the COPP-study (N20.043) (need for supplemental oxygen and/or intensive care admission because of COVID-19 and/or death).

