7. METHODS

7.1 Study parameters/endpoints

7.1.1 Main study parameter/endpoint: WES to detect rare, high impact genetic variants

First, we will evaluate if some children with MIS-C or post-COVID condition have a previously unidentified inborn error of immunity (IEI)

We will use existing diagnostic algorithms to diagnose monogenic inborn errors of immunity in MIS-C or post-COVID condition cases. This means that here, **we will restrict our analysis to pathogenic (class 5) or likely pathogenic (class 4) variants** (as established by the American College of Medical Genetics and Genomics and the Association for Molecular Pathology guideline (33)) **in genes known to be associated with monogenic inborn errors of immunity (IUIS IEI gene set).**

Next, we will do a case-control rare variant association study.

In the subsequent case-control analysis we will focus on determining if a larger proportion of cases with MIS-C or post-COVID condition have rare and presumably deleterious variants in immunological genes than children with an asymptomatic or mild infection.

7.1.2 Secondary study parameters/endpoints: Clinical characteristics and long-term effects of pediatric COVID-19 and MIS-C

We will describe the clinical characteristics of children hospitalized with COVID-19 or MIS-C. Also, we will evaluate the long-term effects of pediatric COVID-19 and MIS-C. A detailed description of the clinical course of MIS-C and post-COVID condition will enable us to make subgroups of patients. For example, children with MIS-C who need inotropic support vs. those who do not. For this purpose, we will use available data from our ongoing nation-wide cohort study of children with COVID-19 or MIS-C in Dutch hospitals (Clinical features of COVID-19 in Pediatric Patients; COPP-study and COPP-IMM study; WHO-CRF with additions). Inclusion in this study is ongoing in 53 hospitals.

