- A link to our website (www.covidkids.nl/grip) where the participant can find information and a video about the procedures in the GRIP study;
- A link that will refer the participant to a short questionnaire in Formdesk. The link to the formdesk form will be unique so we will be able to trace from which group (MIS-C, post-COVID condition, controls) the potential participant belongs

Formdesk form

If the subject wants to participate in the GRIP study, he/she/the parents can fill out their home address, e-mail address and phone number in this questionnaire. By filling out and returning the questionnaire, the subject consents with our research team contacting the subject by phone for a further explanation on the GRIP study.

Information by telephone

Once we receive a filled out questionnaire, the potential participant of the GRIP study will be contacted by phone. During this phone call:

- We will shortly explain the study
- Subjects can ask additional questions

If the parents/patients wish to participate, we will collect the following information during this phone call:

- For cases (MIS-C or post-COVID condition): General practitioner. This is needed to be able to give feedback on the genetic results.
- For controls: we will ask some questions to verify that the participant does not exclude as a control: (approximate) date of prior SARS-CoV-2 infection(s); how the infection was determined; clinical course of prior SARS-CoV-2 infection(s): exclusion as a control if any of the following apply: admission to hospital; occurrence of MIS-C; persistent health problems related to SARS-CoV-2 infection after 12 weeks
- For cases and controls: country in which the parents and grandparents of the child were born. This information is needed for the interpretation of rare genetic variants.

We will discuss with the parents which type of Saliva Collection Kit is most suitable for their child (assisted collection or self-collection, see next paragraph on saliva collection).

If the subject wants to participate in the GRIP study, we will send him/her/the parents an confirmation e-mail again containing the 'Patient Information Form' and links to the instruction materials. We will send them the 'GRIP Saliva Collection Kit' containing the saliva collection kit and the consent form by regular mail (see next paragraph).

Confirmation email

We will send a confirmation email. In this email, we will again link to the information form and instruction materials.

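### Controls are screened for acute COVID-19 severity but post-COVID cases are not, so an excess of variants could be attributed only to a complicated course, not specifically to post-COVID condition

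*Protocol*

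**What the plan says.** **Controls.** Section 2 describes them as "children who were infected with SARS-CoV-2 but did not develop moderate to severe COVID-19, MIS-C or post-COVID condition". Section 3.3 makes this an exclusion for group 3: "Moderate or severe course of COVID-19, as defined in the COPP-study (N20.043) (need for supplemental oxygen and/or intensive care admission because of COVID-19", or death). The telephone screen in section 7.3.1 is wider: "exclusion as a control if any of the following apply: admission to hospital".

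**Post-COVID cases.** The group 2 exclusions in section 3.3 are "other plausible cause of symptoms AND/OR a history compatible with chronic fatigue syndrome prior to infection with SARS-CoV-2", and children with prior MIS-C go to group 1. Neither section 3.2 nor section 3.3 mentions how severe the acute infection was.

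**Source of cases.** Section 3.1 names four sources, the first in these words: "post-COVID condition, will be recruited from the COPP follow-up study 'COPP2". Section 7.1.2 says that COPP participants are invited to this follow-up, and describes COPP as an "ongoing nation-wide cohort study of children with COVID-19 or MIS-C in Dutch hospitals". The other three sources are PoCoCoChi, VINCERO/VINCERE and POCOS.

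**Genetic background.** In support of its hypothesis, section 1 reports that "in a subset of adults with life-threatening COVID-19, inborn errors of type I interferon immunity have been found".

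**Analysis.** Section 9.1 collapses qualifying variants and compares cases with controls. It states no restriction or stratification by acute severity. Sections 7.1.2 and 7.1.3 announce subgroups in general terms, and their examples concern MIS-C.

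**The concern.** A child who needed oxygen and still had symptoms after 12 weeks is an eligible post-COVID case. A child with the same acute illness but no lasting symptoms cannot be a control. The eligibility rules thus tie acute severity to case status, and one case source draws on a hospital cohort.

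The protocol itself treats inborn errors of immunity as relevant to life-threatening acute COVID-19, at least in adults. If the same holds to some degree in children, variants that predispose to severe acute disease would be more frequent in the post-COVID group through those children alone.

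What is at stake is attribution. The hypothesis in section 1 and the main question in sections 3.4 and 9.1 name post-COVID condition. Under section 7.1.3, a positive cluster leads to functional work and to testing of pharmacological agents. A signal carried by acute severity would send that work in a direction that the comparison had not established.

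**Working it through.** **Inputs from section 3.4:** control rate of qualifying variants p0 = 3.7%; design odds ratio 4; 100 cases and 200 controls; Fisher exact test at 0.05. Sidedness is not stated.

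**Inputs not in the protocol (assumptions):** f, the share of post-COVID cases with moderate or severe acute disease; and OR_s, the odds ratio for carrying a qualifying variant in those cases. OR_s is varied over 2, 4 and 5.2. The last two are the protocol's own figures, but they derive from MIS-C, not from acute COVID-19.

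**Step 1: reproduce the plan's figure.** Control odds are 0.037/0.963 = 0.03842. At odds ratio 4 the case odds are 0.15369, so the case rate is 0.15369/1.15369 = 13.32%. Exact enumeration of both binomials with a two-sided Fisher test gives power 0.826. The protocol's overall positive rates with one affected cluster are 0.806 to 0.833, so the figure is reproduced. A one-sided test gives 0.864, which does not fit.

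**Step 2: mix severe-acute children into the case group.** Suppose that there is no other effect. Then

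case rate = f × p_s + (1 − f) × p0,

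where p_s is the carrier rate implied by OR_s. Example with OR_s = 4 and f = 20%: 0.2 × 0.1332 + 0.8 × 0.037 = 0.0562. The apparent odds ratio is (0.0562/0.9438)/0.03842 = 1.55.

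With OR_s = 4, the same Fisher test against 200 controls at 3.7% gives:

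| f | case rate | apparent OR | chance of P<0.05 |
|---|---|---|---|
| 0% | 3.70% | 1.00 | 3.4% |
| 10% | 4.66% | 1.27 | 5.9% |
| 20% | 5.62% | 1.55 | 10.8% |
| 30% | 6.59% | 1.84 | 18.0% |

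**Step 3: vary the second assumption, at f = 20%.**

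| OR_s | apparent OR | chance of P<0.05 |
|---|---|---|
| 2 | 1.19 | 4.9% |
| 4 | 1.55 | 10.8% |
| 5.2 | 1.75 | 15.6% |

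The reference is 3.4%, not 5%, because Fisher's test is conservative at these counts. The direction is upward whenever f > 0 and OR_s > 1. The inflation is small at f of 10% or less. From about 20% it is material if OR_s is near 4 or above, and slight if OR_s is near 2.

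**Step 4: cost of a restricted contrast.** Two-sided Fisher power at odds ratio 4 against 200 controls, if the cases left out are not replaced:

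| cases left | power |
|---|---|
| 100 | 0.826 |
| 95 | 0.807 |
| 90 | 0.804 |
| 80 | 0.766 |
| 70 | 0.732 |

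**The case against.** **The contrast may be intended.** Section 1 also speaks of comparing a complicated with an uncomplicated course, and the summary and section 7.1.1 describe controls as uncomplicated, asymptomatic or mild. Restricting controls to mild disease serves that comparison. This stands, and it limits what a positive result can be said to show.

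**The main question would not be answered wrongly.** A reader might infer that it would. The documents do not support this. If variants raise the risk of severe acute disease and some of those children go on to post-COVID condition, then the post-COVID cases do carry more variants than exposed controls, and yes is the right answer to the question as worded. Acute severity may also lie on the path from variant to post-COVID condition, so removing those children outright would discard part of a real effect. For this reason a change to eligibility is a debatable choice of estimand, not a correction.

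**The size is not known.** COPP2 is one of four sources, and PoCoCoChi recruits at a public test location. COPP also supplies controls, so belonging to COPP does not make a child moderate or severe. The cited genetic link concerns adults with life-threatening disease, whereas the section 3.3 category starts at supplemental oxygen. All of this stands.

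**The control exclusion alone does little.** If 1% to 2% of otherwise eligible controls had such disease and carried variants at 13.3%, keeping them would move the control rate only from 3.7% to about 3.8% to 3.9% (0.02 × 0.1332 + 0.98 × 0.037 = 0.0389). This is also fair: what matters is the share among cases.

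**Subgroups are foreseen, and an analysis plan may add detail.** The subgroup wording is general and commits to no contrast by acute severity. A separate analysis plan, not available here, could contain one. But eligibility is fixed in the protocol, and the limit on attribution follows from it.

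**Conclusion.** The concern holds in a limited form. Acute severity is screened out of the control group and not out of the post-COVID group, and at least one source can supply children with moderate or severe acute disease. An excess in post-COVID cases could therefore partly reflect variants that predispose to severe acute COVID-19. As planned, it can be attributed to a complicated versus an uncomplicated course, but not specifically to post-COVID condition.

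The size cannot be fixed from the protocol. The figures above assume no other effect, a 3.7% background rate, and values of f and OR_s that the protocol does not give. They show what could happen; they do not estimate the bias in this study. The background rate is itself for predicted loss-of-function variants, while section 9.1 also admits missense and in-frame variants.

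One inconsistency needs no assumption: sections 3.3 and 7.3.1 state different acute-severity exclusions for controls.

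**What to change.** 1. Keep eligibility as it is. Classify each post-COVID case by the section 3.3 moderate/severe definition, using the source-study clinical data that sections 7.3.2 and 11.1 already plan to link with consent.
2. In section 9.1, prespecify a post-COVID versus control contrast restricted to cases whose acute infection did not meet that definition. Report the remaining cases as a separate stratum.
3. State that an excess will be attributed to post-COVID condition itself only if it persists in the restricted contrast. Otherwise describe it as a difference between complicated and uncomplicated courses.
4. Reconcile the control exclusion in section 3.3 (oxygen, intensive care or death) with the telephone screen in section 7.3.1 (any hospital admission).

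**Cost.** A few sentences and one derived variable, provided that all four source studies recorded oxygen and intensive-care need, which the protocol does not say. The restricted contrast has somewhat lower power: at odds ratio 4, 0.804 with 90 cases and 0.766 with 80. A non-significant restricted result is therefore not proof that acute severity explains the excess, and should be reported with its confidence interval.
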